#### **2.3.1. Risk Assessment**

Izokibep is a biologic that binds IL-17A with high affinity and with a potency corresponding to clinically tested monoclonal antibodies in terms of blocking the biological activity of IL-17A.

- IL-17A inhibitors, including secukinumab at 10 mg/kg and 30 mg/kg and ixekizumab as well as izokibep at doses up to 160 mg SC, do not appear to have dose-limiting AEs.
- Class effects and potential risks seen with other IL-17 inhibitors have not been identified with izokibep. Given small numbers of subjects treated to date, class effects and potential risks of IL-17 inhibitors will be explicitly monitored (ie, events of special interest) and have been taken into consideration in the development of inclusion and exclusion criteria. These events include candida infections, IBD, and suicidal ideation and behavior risk monitoring.
- Non-serious, mild-to-moderate ISRs are the most common AE reported in association with SC administration of izokibep. These are typically self-resolving, however additional measures to mitigate/manage ISRs include the following:
  - Allow study drug to warm to room temp prior to administration, about 15 to 20 minutes.
  - Administer study drug slowly.
  - Use ice/ice packs following study drug administration.
  - Rotate sites of administration; avoid injecting the same site twice during any visit.

- Use of oral antihistamines.
- Use of acetaminophen or ibuprofen for pain or discomfort.
- Topical corticosteroids may be used for localized erythema, edema, or pruritis.
- No genotoxicity or carcinogenicity is foreseen as izokibep is a protein consisting of natural amino acids. However, since no data are available at this stage of clinical development on possible effects on the reproductive system, the following precautionary measure will be taken:
  - Females of childbearing potential as well as reproductive female partners of male subjects must use an adequate method of contraception while participating in the clinical study until at least 8 weeks after the last dose of study drug. Pregnancy testing will be performed at regular intervals prior to, during treatment, and after the end of treatment (ie, 8 weeks after the last investigational medicinal product [IMP] dosing).

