#### **8.2.11. Suicidal Ideation and Behavior Risk Monitoring**

Subjects with HS may occasionally develop suicidal ideation or behavior. Furthermore, suicidal ideation and behavior has been identified as a potential risk with other IL-17 class products.

Suicidal ideation and behavior will be assessed during the study by trained study personnel using the C-SSRS. The visits at which the C-SSRS assessments will be performed are specified in the SoA ([Section 1.3](#)). The C-SSRS is a standardized and validated instrument developed for the assessment of the severity and frequency of suicidal ideation and behavior (Posner et al, 2011). Subjects respond to standardized clinical questions that are presented in a uniform fashion. The C-SSRS defines 5 subtypes of suicidal ideation and behavior in addition to self-injurious behavior with no suicidal intent. The C-SSRS takes approximately 3 to 10 minutes to complete.

Subjects should be monitored appropriately and observed closely for suicidal ideation and behavior or any other unusual changes in behavior, especially at the beginning and end of the course of study drug. Subjects who experience signs of suicidal ideation and behavior should undergo a risk assessment which may or may not include examination by a mental health care

professional. All factors contributing to suicidal ideation and behavior should be evaluated and consideration should be given to discontinuation of the study drug.

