### **8.3.6. Adverse Events of Special Interest**

Based on the class effects or potential risks with IL-17 inhibitors, the following events of special interest will be monitored:

- Candida infection
- IBD
- Suicidal ideation
- Malignancies
- Major adverse cardiovascular and cerebrovascular events (cerebrovascular accident and transient ischemic attack, non-fatal myocardial infarction or unstable angina, and cardiovascular death)
- TB
- Infections (opportunistic, serious, or fungal only)
- Cytopenias (anemia, neutropenia, lymphopenia, monocytopenia, thrombocytopenia)
- Systemic hypersensitivity reactions.

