## **9.3. Statistical Analyses**

### **9.3.1. General Considerations**

All data collected will be summarized by planned timepoint without imputation. Continuous data will be summarized with count, mean, median, standard deviation, minimum, and maximum. Change from baseline will additionally include standard error. Categorical data will be summarized with count and percent. Time to event data will be summarized with product-limit estimators of median and quartiles.

All hypothesis tests will be reported with 2-sided p-values. All CIs will be 2-sided with nominal 95% coverage. Hypotheses tested will be adjusted to control the familywise error rate in the strong sense at  $\alpha = 0.050$ , 2-sided. All hypothesis tests will use a type I error rate of 5%.

Data will be summarized by planned timepoint, using data collected at the visit. Study day will be calculated as post-baseline date minus randomization date, plus 1 (except that study day for pre-randomization dates will not include the plus 1). Day range windows will not be applied for summaries (but may be applied for protocol deviations). Baseline values will be the last value collected before randomization and change from baseline will be calculated as post-baseline value minus baseline value.

Stratified tests will use the 4 strata from the randomization process. If a subject is incorrectly classified during the randomization process, the analysis will use the correct classification, not the classification used during randomization.

After Week 16, efficacy and safety data will be summarized. Data for subjects who were randomly assigned to receive placebo during the first 16 weeks will be summarized separately from data for subjects who were randomly assigned to receive izokibep during the first 16 weeks.

Subgroup analyses (including, age, race, sex, baseline disease characteristics, geography, concomitant antibiotic use, and other factors) will be reported.

Any deviation from the planned analyses made after breaking the blind will be documented in the clinical study report.

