- Any adverse event where “Please check if this event is an injection site reaction” is checked “Yes” or MedDRA High Level Term = “injection site reactions”.
 - ISRs are mapped to a particular injection/visit based on the following logic:
 - If the ISR occurs on the day of an injection after administration of treatment or prior to the date/time of the next injection, it should be attributed to the visit where the latest injection occurred.
 - If the ISR occurs after administration of treatment at a particular visit and additional injections do not occur, then the ISR should also be attributed to the visit where the latest injection occurred.

6.10.2.2 *Adverse Event of Special Interest (AESI)*

The following AESIs will be included:

- Candida infection
- Inflammatory bowel disease
- Suicidal ideation
- Malignancies
- Major adverse cardiovascular and cerebrovascular events (MACE) (cerebrovascular accident and transient ischemic attack, non-fatal myocardial infarction or unstable angina, and cardiovascular death)
- Tuberculosis
- Infections (opportunistic, serious, or fungal only)
- Cytopenias (anemia, neutropenia, lymphopenia, monocytopenia, thrombocytopenia)
- Systemic hypersensitivity reaction

Adverse events of special interest will be identified manually. After all data are entered into the database, a list of all unique preferred terms (PTs) will be generated. ACELYRIN pharmacovigilance and clinical development representatives will review the list and determine which are TEAEs of special interest in each category listed above. This determination will be documented in a memo, signed and dated before database lock for the final analysis and stored in the study trial master file. The memo will specify the subjects and preferred terms to be included as AESIs, including justification for including or excluding events as appropriate. The database will not be locked until the memo is finalized and signed.

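### The AESI category covers suicidal ideation but not behavior, and the SAP plans no post-baseline C-SSRS output

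*SAP*

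**What the plan says.** **The risk.** Protocol 2.3.1 says IL-17 class effects will be explicitly monitored and identifies them with events of special interest: "These events include candida infections, IBD, and suicidal ideation and behavior risk monitoring". Protocol 8.2.11 states that "suicidal ideation and behavior has been identified as a potential risk with other IL-17 class products".

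**The AESI list.** Protocol 8.3.6, which defines the AESIs, has the entry "Suicidal ideation" and does not mention behavior. SAP 6.10.2.2 repeats that entry. Identification is manual: once the data are in, sponsor pharmacovigilance and clinical development staff take the unique preferred terms, "review the list and determine which are TEAEs of special interest in each category listed above", and record the result in a signed memo before database lock, "including justification for including or excluding events as appropriate". SAP 9.8.2 then produces an AESI table by SOC and PT and an AESI listing.

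**The instrument.** Protocol 8.2.11: "Suicidal ideation and behavior will be assessed during the study by trained study personnel using the C-SSRS". The schedule of activities places it at screening, Day 1, Weeks 4, 8, 12, 16, 20, 24, 32 and 40, and end of treatment, with the since-last-visit version used after screening. Protocol 9.3.1 says: "All data collected will be summarized by planned timepoint without imputation". In SAP 9.3 the C-SSRS appears only as baseline ideation (lifetime and past 6 months). SAP 9.8 has no C-SSRS output, and 9.8.7 plans no further endpoint analyses. SAP Section 5 announces limited safety summaries and names laboratory data, ECGs, vital signs and physical examination as not summarized. The C-SSRS is not named.

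**The concern.** The incidence of events of interest belongs to the secondary safety objective in both documents (protocol Section 3, SAP 3.2), so the scope of each AESI category shapes a stated result. A reader of the AESI table would take it as the account of suicidality under an IL-17A inhibitor. If the category is applied as written, that account can stop at ideation and omit the more severe form of the risk.

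The C-SSRS half is separate. Subjects complete a dedicated questionnaire throughout treatment, and the report as planned gives no post-dose result from it. The plan also does not say that this was decided.

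**Working it through.** No arithmetic applies. The documents give no rate of suicidal events, and any assumed rate would describe how often such events occur, not how often the plan would fail to show them. The check is a comparison of texts.

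**Step 1: scope of the category.**

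| Place | Scope |
|---|---|
| Protocol 2.3.1, risks monitored as events of special interest | ideation and behavior |
| Protocol 8.2.11, class risk | ideation and behavior |
| Protocol 10.3.5, examples of reasons to stop drug | C-SSRS items 4 or 5, or any behavior |
| Protocol 8.3.6, AESI list | ideation |
| SAP 6.10.2.2, AESI list | ideation |

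The mismatch begins inside the protocol, and the SAP inherits the narrower wording. Three other entries in the same list (cardiovascular and cerebrovascular events, infections, cytopenias) spell out their scope in parentheses. The suicidality entry does not, so a literal reading is a natural one.

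**Step 2: what the narrow wording can affect.** It affects the AESI table and the AESI listing in SAP 9.8.2. The other outputs there do not use the category: TEAEs by SOC and PT, serious TEAEs, TEAEs leading to discontinuation, the listing of all AEs and the listing of deaths. A suicide attempt recorded as an AE appears in those whatever the memo decides.

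**Step 3: can the AE outputs stand in for the C-SSRS?** Only in part.
- Protocol 8.2.11 responds to signs of suicidality with a risk assessment and consideration of stopping drug. It does not say the finding must be recorded as an AE.
- Protocol 10.3.1 makes a safety-assessment finding an AE when the investigator judges it clinically significant.
- Protocol 10.3.5 does list items 4 or 5 and any behavior under its AE heading, as examples that could lead to discontinuation. The serious positives should therefore usually reach the AE data.
- Ideation short of items 4 and 5 has no such pointer.

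**Step 4: is the omission declared?** Other analyses dropped for the abbreviated report are named where they are dropped: the four data types in SAP Section 5, subgroups in 8.8 and 9.11, protocol deviations in 9.2, sensitivity analyses in 9.5.1. For the C-SSRS there is only the general statement about limited summaries and the catch-all in 9.8.7.

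**The case against.** The strongest reply is that the SAP does what the protocol's own AESI section says, and that the process makes a real omission unlikely. Medically qualified staff review terms by hand and must document why events are included or excluded, so leaving out a suicide attempt would probably take a deliberate decision. That stands. What remains is that nothing in the written category requires inclusion.

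It can also be said that protocol 2.3.1 borrows the title of the monitoring procedure in 8.2.11 and is not naming an AESI category. That is a possible reading. On it, the sentence points to the procedure, and the procedure's instrument is what has no post-baseline output.

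On the C-SSRS, no specific analysis was promised. It is not an endpoint, protocol 9.3.5 does not name it, and the only commitment is the general sentence in 9.3.1. It also serves subject care during the trial whether or not it is tabulated. The table shells are in a separate document that was not available and could contain a listing. All of this stands and keeps the severity low.

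A reader might infer three stronger things that the documents do not support:
- **Suicidal events will go unreported.** They will not if recorded as AEs or SAEs. Protocol 10.3.1 also requires overdoses with possible suicidal or self-harming intent to be reported regardless of consequences.
- **The SAP departs from the protocol's AESI definition.** It repeats protocol 8.3.6.
- **The C-SSRS was dropped covertly.** Section 5 is not an exhaustive list, and it does announce limited safety summaries.

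**Conclusion.** The point holds as a low-severity reporting improvement. The AESI category as worded is narrower than the risk described in protocol 2.3.1 and 8.2.11, and the SAP text contains no post-baseline output from the instrument the protocol assigns to that risk. The effect is confined to the AESI table, the AESI listing and the C-SSRS results. No recorded safety event is lost, and no efficacy or alpha-controlled analysis is touched.

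The first half rests on a literal reading of the category, which the memo could override. The second rests on the SAP text alone, since the shells were not seen. The documents do not allow the practical effect to be put in numbers.

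**What to change.** 1. In SAP 6.10.2.2, rename the category *Suicidal ideation and behavior* and apply that scope in the memo signed before database lock. The AESI table is by SOC and PT, so ideation and behavior terms would still be shown separately. The same wording can go into protocol 8.3.6 if the protocol is amended for other reasons. No amendment is needed for this alone.
2. Add one short descriptive listing, or a table by arm and period, of subjects with any post-baseline C-SSRS ideation or behavior. Flag items 4 or 5, any behavior, and whether a matching AE was recorded. Items 4 or 5 and behavior are the cut already used in protocol 10.3.5.

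The cost is one label change and a little programming on data already collected. The abbreviated report already keeps a data-based table of liver criteria (SAP 9.8.3.1), so one more short safety output fits its scope. If the sponsor prefers not to add it, naming the C-SSRS in SAP Section 5 among the data not summarized would at least make the decision visible.

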6.10.3 Clinical Laboratory Assessments

All laboratory data will be converted to SI units. The change from baseline at each visit until Week 52 for all hematology, clinical chemistry, routine urinalysis, and other tests will be calculated as: *the current visit value - the baseline value*.

All quantitative hematology and clinical chemistry laboratory test values at each assessed visit through Week 52 will be compared with the relevant reference range in SI units and categorized as:

- Low: Below the lower limit of the reference range.
- Normal: Within the reference range (upper and lower limits included).
- High: Above the upper limit of the reference range.

Clinical laboratory results will not be summarized or listed for the purposes of abbreviated CSR, but will be available in the analysis datasets.

6.10.3.1 Liver Function Tests

Subjects who met any (1 or more) of the following liver function test (LFT) criteria at any point after starting study treatment and prior to Week 16 will be included in consideration of potential drug-induced liver injury (DILI) in Period 1:

- Alanine Transaminase (ALT) or Aspartate Transferase (AST) $\geq 5 \times$ upper limit of normal (ULN) at any time
- ALT or AST $\geq 3 \times$ ULN at all (2 or more) assessments in a span of ≥ 4 weeks
- ALT or AST $\geq 3 \times$ ULN and total bilirubin $\geq 2 \times$ ULN ($>35\%$ direct bilirubin) simultaneously at any time
- ALT or AST $\geq 3 \times$ ULN and international normalized ratio (INR) ≥ 1.5 simultaneously at any time
- ALT or AST $\geq 3 \times$ ULN at any time during the study and weekly assessments after this finding are not available for at least 4 weeks
- ALT or AST $\geq 3 \times$ ULN associated with symptoms (new or worsening) believed to be related to liver injury or hypersensitivity at any time

To determine subjects who meet the last criterion, a listing of all subjects who have at least 1 ALT or AST $\geq 3 \times$ ULN at any time after starting study treatment and prior to Week 16, and who do not meet any of the first 5 criteria, will be reviewed by ACELYRIN pharmacovigilance and clinical development representatives along with a listing of all AEs reported by such subjects. In consideration of the investigator's causality assessment, the medical professionals will assess whether any AE is believed to be related to liver injury or hypersensitivity and, if so, whether the elevated ALT or AST is in temporal association with the AE. Any subjects who meet these criteria will be included on a memo that is finalized prior to database lock and that will be filed in the trial master file (TMF).

If there is crossover between Period 1 and Period 2 in any of the instances listed above that require several events over a particular time-span, the LFT flag will be assigned to the period in which the first finding occurs.

Hy's Law is met when all 3 of the following criteria is met simultaneously (at the same draw):

- ALT or AST is $\geq 3 \times$ ULN
- Total bilirubin $\geq 2 \times$ ULN

- Alkaline Phosphatase (ALP) is <2 x ULN

At each assessment through Week 16, subjects will be classified as meeting Hy's Law or not meeting Hy's Law.

An analogous approach will be used for evaluating Period 2 for potential DILI. Visits after Week 16 will be considered. Only subjects who took at least one dose of treatment in Period 2 are evaluated for Period 2 potential DILI.

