9.8.3.1 Liver Function Tests

A summary table will present the count/proportion of subjects who meet each of the 6 criteria for consideration of potential DILI and subjects meeting Hy's Law at any time through Week 16, and, separately, for any time through Week 52. A similar summary table will be created for Period 2 only, for just the subjects in the SAF with at least one dose of study treatment in Period 2. Baseline results will not be included in the table; only post-baseline liver function test values are flagged.

Potential liver toxicity will be assessed by listing subjects who met potential drug induced liver injury (pDILI) criteria as described in the protocol and by summarizing subjects who met Hy's Law for the SAF.

For subjects who meet any of the 6 criteria for consideration of potential DILI and subjects being classified as meeting Hy's Law or not meeting Hy's Law, all LFT results at any time through Week 52 will be listed, sorted by subject and date. Listing will include subject, treatment assignment, ALT, AST, ALP, bilirubin and INR, along with specific criterion met for DILI as well as met/not met Hy's Law. Subjects who met the criteria prior to or at Week 16, and anytime in Period 2 will be flagged.

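### SAP 6.10.3.1, read literally, leaves the pre-dose Week 16 liver chemistry out of both the Period 1 and Period 2 potential-DILI windows, contrary to SAP 6.2.5 and 9.8.3.1 (minor)

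*SAP*

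**What the plan says.** SAP 6.10.3.1 lists six criteria for potential drug-induced liver injury (DILI). A subject who meets any of them "after starting study treatment and prior to Week 16 will be included in consideration of potential drug-induced liver injury (DILI) in Period 1". Criterion 6 (a transaminase elevation with related symptoms) is settled by medical review of a listing. That listing is limited to subjects with an elevation "at any time after starting study treatment and prior to Week 16, and who do not meet any of the first 5 criteria". For Period 2 the section says "Visits after Week 16 will be considered", and only subjects with at least one Period 2 dose are evaluated.

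The same section treats Hy's Law differently: "At each assessment through Week 16, subjects will be classified as meeting" it or not.

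The reporting section, SAP 9.8.3.1, also includes Week 16. It states: "A summary table will present the count/proportion of subjects who meet each of the 6 criteria for consideration of potential DILI", and its window is "at any time through Week 16, and, separately, for any time through Week 52". For the accompanying listing: "Subjects who met the criteria prior to or at Week 16, and anytime in Period 2 will be flagged".

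SAP 6.2.5 ends Period 1 once the Week 16 assessments are done and before Period 2 dosing. Protocol section 8 has assessments done before study drug is given unless otherwise specified, and the Schedule of Activities (Protocol 1.3) includes chemistry at Week 16.

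**The concern.** Two parts of the SAP give different instructions for the same safety counts. Week 16 is the last scheduled chemistry draw before placebo subjects start izokibep, so it is the last point at which liver chemistry can be compared between randomized arms. SAP 5 and 9.8.3 drop every other summary of clinical laboratory data from the abbreviated report, which leaves the 9.8.3.1 table as the only planned between-arm summary of liver chemistry. If its Period 1 flags are built from the literal 6.10.3.1 window, an elevation first seen at Week 16 could be missing from the placebo-controlled comparison or be counted in the wrong period.

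**Working it through.** No figure in the plan needs reproducing. The check sets the window statements side by side, traces each type of criterion, and counts draws.

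**1. Where each rule puts the pre-dose Week 16 sample**

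| Place | Window | Week 16 sample |
|---|---|---|
| SAP 6.10.3.1, Period 1 flags | before Week 16 | out |
| SAP 6.10.3.1, criterion-6 review listing | before Week 16 | out |
| SAP 6.10.3.1, Period 2 flags | after Week 16, Period 2 dose required | out |
| SAP 6.10.3.1, Hy's Law | through Week 16 | in Period 1 |
| SAP 6.2.5, Period 1 | until Week 16 assessments are complete, before Period 2 dosing | in Period 1 |
| SAP 9.8.3.1, table of six criteria | through Week 16 | in |
| SAP 9.8.3.1, listing flag | before or at Week 16 | in |

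**2. Consequence by criterion on the literal reading, when the first elevation is at Week 16**

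- *Criteria 1, 3 and 4 (one draw is enough).* There is no Period 1 flag. If later values are normal, there is no Period 2 flag either. If a later value still qualifies and is used, the flag falls in Period 2. For a placebo subject who took the Week 16 dose, that means under izokibep. The crossover rule does not repair this, because it covers only criteria that need several events over a time span. A subject with no Period 2 dose is evaluated in neither period.
- *Criteria 2 and 5 (several assessments).* The crossover rule assigns the flag to the period in which the earliest qualifying value occurs. With the 6.2.5 boundary that is Period 1, so these are recoverable.
- *Criterion 6.* The subject does not enter the Period 1 review listing. No other window statement in the SAP corrects that listing.

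**3. Can criterion 5 act as a safety net?** It applies when "weekly assessments after this finding are not available for at least 4 weeks". On the schedule alone, the next chemistry after Week 16 is at Week 24 or later (the row is broken in the extracted text and reads as Week 24 or Week 32). The gap is at least 24 − 16 = 8 weeks, which would seem to satisfy criterion 5. But for ALT or AST at or above 3 × ULN, Protocol 10.5 calls for repeat tests within 24 to 72 hours (24 hours if bilirubin or INR is also raised) and then twice-weekly monitoring. A subject followed that way has the weekly values and need not meet criterion 5, so it cannot be relied on.

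**4. Size**

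- Scheduled post-baseline chemistry in Period 1: Weeks 4, 8, 12 and 16, which is 4 draws. The literal window uses 3 of 4. This counts scheduled draws, not changed flags.
- Planned subjects per arm: 125 (SAP 4.1). Change in an arm's Period 1 rate = k/125, where k is the number of subjects first meeting a criterion at Week 16. The documents give no liver event rates, so k is an assumption: k = 0, 1, 2, 3 gives 0, 0.8, 1.6, 2.4 percentage points.

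**The case against.** The best reply is that the SAP already resolves the question. The Period 1 sentence uses a defined term, and 6.2.5 defines it to include the Week 16 assessments. The output specification in 9.8.3.1 includes Week 16 twice. Elsewhere the SAP uses before-Week-16 wording loosely for Period 1, for example in the disposition list in 9.1 and the exposure formula in 6.10.1. If the phrase means before the Week 16 dose, the sections agree.

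Much of this stands. A programmer who reads all the sections would probably include Week 16, so the text supports saying that counts could be wrong, not that they will be. The loose-usage argument is weaker. SAP Table 3 counts a subject as discontinued before Week 16 only if the Week 16 visit is missing. Where the SAP wants the dose as boundary it says so, as for Period 1 adverse events in 6.10.2. The reply also does not reach the criterion-6 listing, which has no second window statement.

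The misattribution case needs a later qualifying value to be used. SAP 6.2.2 excludes most unscheduled results from analyses, although 6.10.3.1 speaks of findings at any time and criterion 5 makes little sense without unscheduled draws. It is a possibility, not an expected result.

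A reader might infer that liver signals would be lost to the trial. The documents do not support that. Hy's Law already includes Week 16, and the through-Week-52 table still captures criteria 1 to 5. Subjects meeting stopping criteria must be reported within 24 hours, clinically significant laboratory changes are recorded as adverse events and tabulated by arm, and the values stay in the analysis datasets.

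**Conclusion.** The inconsistency is real, and the derivation rule is wrong as written: on its literal terms the Week 16 chemistry is in neither period. The severity is minor. It affects descriptive counts in one table and the criterion-6 review behind it. No p-value, efficacy result or error rate is involved.

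Two inferences should be avoided. The 3-of-4 draw count does not mean that a quarter of liver findings would be lost. The 0.8 to 2.4 point range is not an estimate of bias, because it rests on assumed counts of one to three subjects per arm, and zero is possible. The conclusion assumes that the Week 16 sample is drawn before dosing, as Protocol section 8 directs, and that the chemistry row of the schedule is read correctly as Weeks 4, 8, 12 and 16.

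**What to change.** In SAP 6.10.3.1, in both the Period 1 flag sentence and the criterion-6 listing, replace the before-Week-16 cut with: *through the Week 16 assessment, before the first Period 2 dose (or through the last Period 1 assessment if there is no Period 2 dose)*. Define the Period 2 window as assessments after the first Period 2 dose. This brings the derivation into line with SAP 6.2.5 and 9.8.3.1.

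The cost is three short wording changes and the matching derivation code, with no new data. It should be done before the criterion-6 listing is run, because the memo from that review is finalized before database lock.
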